### **8.2.4.2 Disease Free Survival**

Kaplan-Meier method will be used to estimate the disease free survival rates at 1, 3 and 5 years among patients treated with combined Pembrolizumab, radiation therapy and +/- Cisplatin. 95% CI of these rates will be provided. These survival rates at 1 year will be estimated and compared with historical data (RTOG 9501: 65.4% in CRT and 68.8% in RT) via the one-sample exact test, point and confidence interval estimation. We will also use the log-rank test and Cox model to compare the DFS between the trial data and the historical data if patient level data obtained from RTOG 9501. An interim analysis will be done throughout study at the PI and statistician discretion.

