#### **5.3 Stratification**

After surgical resection, patients will be stratified into two groups: high risk patients with proven positive surgical margins or extracapsular extension of lymph nodes or intermediate risk including all patients not meeting criteria for high risk. There is a small chance that although patients are identified clinically to require radiation prior to surgery, that the pathology will deem the patient to be low risk and radiation would not be considered standard of care. In the event, the investigator feels it is not in the best interest of patient to administer radiation (or radiation would not be considered standard of care), then patient may be withdrawn from the study.

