## **5.7 Subject Withdrawal/Discontinuation Criteria**

Subjects may withdraw consent at any time for any reason or be dropped from the trial at the discretion of the investigator should any untoward effect occur. In addition, a subject may be withdrawn by the investigator or the Sponsor if enrollment into the trial is inappropriate, the trial plan is violated, or for administrative and/or other safety reasons. Specific details regarding discontinuation or withdrawal are provided in Section 7.1.4 – Other Procedures.

A subject must be discontinued from the trial for any of the following reasons:

- The subject or legal representative (such as a parent or legal guardian) withdraws consent.
- Confirmed radiographic disease progression
- Unacceptable adverse experiences as described in Section 5.2.1.2

- Intercurrent illness that prevents further administration of treatment
- Investigator's decision to withdraw the subject
- The subject has a confirmed positive serum pregnancy test
- Noncompliance with trial treatment or procedure requirements
- The subject is lost to follow-up
- Administrative reasons

The End of Treatment and Follow-up visit procedures are listed in Section 6 (Protocol Flow Chart) and Section 7.1.5 (Visit Requirements). After the end of treatment, each subject will be followed for 30 days for adverse event monitoring (serious adverse events will be collected for 90 days after the end of treatment as described in Section 7.2.3.1). Subjects who discontinue for reasons other than progressive disease will have post-treatment follow-up for disease status until disease progression, initiating a non-study cancer treatment, withdrawing consent or becoming lost to follow-up. After documented disease progression each subject may be followed by telephone or in person for overall survival until death, withdrawal of consent, or the end of the study, whichever occurs first.

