### **5.8 Subject Replacement Strategy**

Patients who are unfit or unwilling to continue study after resection will be replaced. Patients who choose not to undergo surgical resection after initial dose of Pembrolizumab will be replaced. In addition, any patient who does not complete at least 1 week of adjuvant treatment will also be replaced.

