### 8.1.3 Power and Sample Size

Based upon RTOG 9501, we expect that DFS at 1 year and 3 years will be 65.4% and 53.5% respectively for patients with high risk features undergoing CRT. We expect to reach similar DFS in this study. We expect that at least 50% of patients (~40 patients) based on defined inclusion criteria will have high risk disease confirmed at resection (+ECE or + margins). With an expected sample size of at least N=40 in the CRT arm, and adding Pembrolizumab to Cisplatin and radiation, we expect to reach over 80% power to detect an increase of 21% in DFS at year 1 (86% DFS compared to 65% at 1 year) using the one-sample exact test at significance level, alpha=0.025 (one-sided). In comparison, assuming that we will reach a similar 1 year DFS of 68.8% in the radiation alone arm, by adding Pembrolizumab, and assuming N=40, we expect to reach over 80% power to detect an increase of 19% in DFS at 1 year (88% DFS compared to 69% at 1 year). Every effort will be made to ensure that we have 40 patients either reached the DFS endpoints or were followed for at least one year without disease recurrence in both strata.

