### 8.2.2 Efficacy Endpoints

#### Primary Endpoint

Disease Free Survival (DFS): measured from the time of treatment allocation to the time of discovery of the first evidence after treatment of any tumor (local, regional, metastatic, or second primary) or death from any cause. DFS at 1 and 3 years will be the primary efficacy endpoints.

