#### Secondary Endpoints

Overall Survival (OS): defined as the time from randomization to death due to any cause. Subjects without documented death at the time of the final analysis will be censored at the date of the last follow-up. OS at 1 and 3 years will be used as secondary endpoints.

Locoregional Control: failure was defined as the reappearance of tumor in the original tumor bed or the development of cervical-node metastases after treatment.

Biomarker analysis including proportion of T cell population subsets before and after immunotherapy both in tumor tissue and peripheral blood.

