### **8.2.3.2 Efficacy Analysis Population**

The analysis of primary efficacy endpoints are based on all patients who received  $\geq 1$  dose of Pembrolizumab. Subjects will be included in the treatment group to which they are stratified after resection.

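### Does the missing DFS censoring rule leave the 1-year comparison with RTOG 9501 undetermined?

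*Combined protocol and SAP*

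**What the plan says.** All references are to the combined protocol and SAP.

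- **Endpoint (8.2.2).** DFS runs from treatment allocation to first tumour of any kind or death, and "DFS at 1 and 3 years will be the primary efficacy endpoints". No censoring date is given. For overall survival there is one: "Subjects without documented death at the time of the final analysis will be censored at the date of the last follow-up".
- **Population (8.2.3.2, and likewise 8.1.2).** "The analysis of primary efficacy endpoints are based on all patients who received" at least one dose of pembrolizumab, grouped by the stratum set after resection.
- **Method (8.2.4.2).** Kaplan-Meier rates with 95% confidence intervals are planned for patients given pembrolizumab and radiation, with or without cisplatin. The 1-year rates are "compared with historical data (RTOG 9501: 65.4% in CRT and 68.8% in RT) via the one-sample exact test, point and confidence interval estimation".
- **Sample size (8.1.3).** The test is one-sided at 0.025 with 40 patients per stratum. The investigators' stated aim is: "we have 40 patients either reached the DFS endpoints or were followed for at least one year without disease recurrence in both strata".
- **Departures.** Section 5.8: "Patients who are unfit or unwilling to continue study after resection will be replaced", as will anyone who does not complete one week of adjuvant treatment. Section 5.3: if pathology shows low risk and radiation is not appropriate, "then patient may be withdrawn from the study". Section 5.7: patients who stop for reasons other than progression "will have post-treatment follow-up for disease status until disease progression, initiating a non-study cancer treatment, withdrawing consent or becoming lost to follow-up".

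**The concern.** The exact test has no place for a censored time. A patient who received the pre-surgical dose, was resected and stratified, and then left belongs to the population of 8.2.3.2. If that patient starts cancer treatment elsewhere, follow-up for relapse stops under 5.7 and only survival contacts continue under 7.1.5.4.1. The 1-year DFS status is then unknown, and the plan does not say whether to count it as failure, leave it out or count it as success.

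Kaplan-Meier does not settle this without a date. If the overall-survival rule were borrowed, later survival contacts would carry such a patient past 1 year as disease-free. In an open-label trial with historical controls, a rule left open could in principle be chosen after the results are known, and it affects the primary efficacy comparison in both strata.

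**Working it through.** **Inputs.** Null 1-year DFS is 68.8% (radiation, RT) and 65.4% (chemoradiation, CRT), from 8.2.4.2. Targets are 88% and 86%, with one-sided alpha 0.025 and N = 40 per stratum, from 8.1.3. The number *k* of event-free patients with unknown 1-year status is assumed, because the documents give none.

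**Step 1: the plan's own figure.** The critical value c(n) is the smallest r with P(X ≥ r) ≤ 0.025 for X ~ Bin(n, p0).
- RT: c(40) = 34. Type I error P(X ≥ 34 | 0.688) = 1.63%; power P(X ≥ 34 | 0.88) = 80.2%.
- CRT: c(40) = 33. Type I error 1.41%; power 81.1%.

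Both agree with the stated power of over 80%.

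**Step 2: add k unknown patients to 40 known ones.** Let X ~ Bin(40, p) be the number disease-free among the 40. The test rejects if:
- unknowns are failures: X ≥ c(40+k)
- unknowns are left out: X ≥ c(40)
- unknowns are disease-free: X ≥ c(40+k) − k

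The critical values for n = 41, 42, 43, 44 are 35, 36, 36, 37 (RT) and 34, 34, 35, 36 (CRT).

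| k | RT power: failure / left out / disease-free | RT type I error, disease-free | CRT power: failure / left out / disease-free | CRT type I error, disease-free |
|---|---|---|---|---|
| 1 | 65 / 80 / 80% | 1.6% | 68 / 81 / 81% | 1.4% |
| 2 | 47 / 80 / 80% | 1.6% | 68 / 81 / 90% | 3.4% |
| 3 | 47 / 80 / 90% | 4.0% | 50 / 81 / 90% | 3.4% |
| 4 | 28 / 80 / 90% | 4.0% | 32 / 81 / 90% | 3.4% |

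Example, RT with 34 of 40 disease-free and 3 unknown: 34/43 gives p = 0.096, 34/40 gives p = 0.016, and 37/43 gives p = 0.008.

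So the counting rule can change the verdict. The type I error passes 2.5% only when unknowns are counted as disease-free, and only for k ≥ 3 (RT) or k ≥ 2 (CRT).

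**Step 3: which counts does the plan support?**
- *Left out.* Section 8.1.3 aims at 40 patients per stratum with an event or a full year of follow-up. Section 5.8 replaces those who leave early. Section 8.2.4.2 describes the estimates as those of patients given the combination. Together these describe a test in patients with known status.
- *Kaplan-Meier.* It is already planned at 1 year with a 95% interval, and the comparison is to include point and interval estimates. The usual convention is to censor at the last disease assessment. Simulation (exponential DFS, 40 patients followed through 1 year plus k = 1 to 4 censored at weeks 4 to 8, log-log interval, 20,000 runs per setting) gave power of 80.0-80.6% (RT) and 80.7-81.4% (CRT), with type I error of 1.5-1.7% and 1.3-1.5%.
- *All failures or all disease-free.* No section proposes either.

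The two counts with support in the text therefore agree. With about 7% loss spread over the first year instead, simulation showed Kaplan-Meier gaining about 2 points of power over leaving patients out and removing less than 1 point of bias.

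**The case for a change.** The strongest reply is that 8.1.2 and 8.2.3.2 say all dosed patients, and that 8.1.3 promises only an effort, not an exclusion. Leaving patients out then conflicts with the stated population. One unknown patient counted as a failure already cuts power to 65% (RT) or 68% (CRT). A DFS censoring sentence would cost nothing.

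Part of this stands. The sections do point to different denominators, and a DFS censoring date is not written. If the unknowns fall inside the 40 rather than being replaced, power at k = 3 is 34/72/85% for RT and 39/75/86% for CRT. Even leaving them out then costs power, but that is the price of lost patients, and a censoring sentence would not recover their outcomes.

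The rest is weaker. It is not settled that replaced or withdrawn patients stay in the test, since 8.2.4.2 describes patients who received the combination. Loss of relapse status is also narrower than it first appears. Section 5.7 keeps patients who stop treatment without progression under disease follow-up unless they start other cancer treatment, withdraw consent or are lost. Sections 7.1.2.6.3 and 7.1.5.4 plan relapse follow-up for 5 years, by phone if needed. Deaths, which are DFS events, are still captured in survival follow-up.

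One possible remedy, switching from the exact test to Kaplan-Meier as soon as one patient is censored early, would make the primary method depend on the data. Reasonable statisticians would differ on that.

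**Conclusion.** The omission is real but is missing detail, not a flaw in the design. The plan names a method that handles censoring, the convention for the date is standard, and an analyst who applies it, or who tests the patients with known status, keeps about 80% (RT) and 81% (CRT) power with type I error below 2.5%. The spread of 47%, 80% and 90% is an illustration. It rests on an assumed 3 unknown patients added to 40 known ones, and its ends come from two extreme counts that the documents do not adopt.

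The conclusion assumes that replacement delivers about 40 patients per stratum with known 1-year status, that early losses are few, and that those lost do not differ greatly from the rest. The last point is least secure for patients unfit after surgery, so readers of the results should look at how many were censored before 1 year and why. The trial is a non-randomised phase II study whose DFS objectives are framed as estimation, which further limits what turns on a single pass-or-fail verdict.

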#### 4.2.3.2 Efficacy Endpoints

This is a phase II non-randomized study and therefore will rely on historical controls for the primary efficacy endpoint of disease free survival (DFS) in resected high risk HNSCC. Based on the pivotal RTOG 9501 and EORTC 22931 adjuvant studies, disease free survival at 1 year was approximately 66% and 76% respectively for the CRT arms and 58% and 72% respectively for radiation only arms (See table). The 3 year estimates are somewhat closer between the two studies.

Study Group	RTOG 9501		EORTC 22931	
	RT	CRT	RT	CRT
Disease Free Survival 1 year	58%	66%	72%	76%
Disease Free Survival 3 year	37%	47%	40%	57%

There were several differences in these studies including number of lymph nodes involved (94% had  $\geq 2$

lymph nodes in RTOG versus only 57% in EORTC) and the number of patients with at least 1 high risk feature (ECE or positive margins) was also different (approximately 70% of the patients in the EORTC and 59% of RTOG

18MAR2021

study) which may account for these differences.

Based on phase I data, Pembrolizumab resulted in response rates up to 46% at least in those patients positive for PD-L1. Therefore, we expect that the addition of Pembrolizumab will significantly reduce the chance of relapse in this population and therefore, will result in improved DFS. Most locoregional relapses (the most common cause of death in this group) occur within the first year. Therefore, our primary and secondary endpoints respectively will be DFS at 1 and 3 years, which will reflect early and late relapse. Our historical baseline will be based off the RTOG 9501 data due to the fact that entry criteria included either ECE, positive margins or  $\geq 2$  lymph nodes all of which are considered to be either high risk or high-intermediate risk which is the group we are most interested in for this study and encompasses our inclusion criteria.

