#### **8.2.4.3 Overall Survival**

Kaplan-Meier method will be used to estimate the overall survival rates at 1, 3 and 5 years among patients treated with combined Pembrolizumab, radiation therapy and +/- Cisplatin. 95% CI of these rates will be provided. These survival rates will be compared with historical data using the log-rank test. We will also use Cox model to compare the historical data if patient level data obtained from RTOG 9501.

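### The patient-level comparison with RTOG 9501 specifies no case-mix control beyond the risk split, so a difference in nodal burden could be read as a pembrolizumab effect

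*Combined protocol and SAP*

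**What the plan says.** Section 8.2.4.2 tests 1-year DFS against fixed RTOG 9501 rates (65.4% for CRT, 68.8% for RT) with a one-sample exact test. It then adds "We will also use the log-rank test and Cox model to compare the DFS between the trial data and the historical data", on the condition "if patient level data obtained from RTOG 9501". Section 8.2.4.3 compares OS with historical data by log-rank and adds "We will also use Cox model to compare the historical data if patient level data obtained from RTOG 9501". Neither section lists covariates, weighting, matching or a restriction of the RTOG patients.

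The one case-mix control is risk group. Section 5.3 calls patients with ECE or positive margins high risk and all others intermediate. Section 8.2.3.2 analyses patients by that post-resection group. Section 8.1.2 tabulates RTOG 9501 rates for matching subsets, yet quotes the whole-arm 66% and 58% beside its own log-rank sentence.

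Section 4.2.3.2 gives 1-year DFS in RTOG 9501 and EORTC 22931 as "66% and 76% respectively for the CRT arms" and "58% and 72% respectively for radiation only arms". It remarks: "There were several differences in these studies including number of lymph nodes involved", and suggests tentatively that nodal involvement and the share with ECE or positive margins may explain the gaps.

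**The concern.** The comparison is not randomised. A log-rank test cannot adjust for prognosis, and a Cox model containing only trial versus historical membership does no better. The primary DFS hypotheses in section 3.1 are framed against historic data, and individual records are the only route to adjustment, because a test against a fixed rate has none.

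Nodal count is the specific gap. Section 4.2.3.2 describes RTOG 9501 entry as ECE, positive margins or at least 2 nodes, so an RTOG patient without ECE or positive margins entered on nodes. Section 5.1.2 of this trial admits T4 disease and T3 oral cavity disease with any N stage. Its intermediate group can therefore hold patients with 0-1 positive nodes who have no RTOG counterpart. Splitting by risk group does not remove that difference.

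**Working it through.** **The plan's own figure.** Section 8.1.3 claims over 80% power with 40 patients per stratum at one-sided 0.025. Exact binomial:
- CRT: success at 33/40 or more; type I error 0.014 at 65.4%, power 0.811 at 86%.
- RT: success at 34/40 or more; type I error 0.016 at 68.8%, power 0.802 at 88%.

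Both reproduce. These tests are not in dispute here.

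**Gaps in the section 4.2.3.2 table (EORTC minus RTOG).**
- CRT: 76 − 66 = 10 points at 1 year; 57 − 47 = 10 at 3 years.
- RT: 72 − 58 = 14 points at 1 year; 40 − 37 = 3 at 3 years.

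The CRT gap is 10/21 = 48% of the 21-point improvement the trial is sized to detect.

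**Which factor could explain them.** Nodal burden fits: 94% had 2 or more "lymph nodes in RTOG versus only 57% in EORTC", and RTOG had the worse DFS. The ECE/margin share ("approximately 70% of the patients in the EORTC and 59% of RTOG") runs the opposite way, since EORTC had more such patients and better DFS. Nodal count is the documented candidate.

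**Historical sample sizes (assumed, back-calculated from the 1-year intervals in section 8.1.2).** SE = (upper − lower)/3.92; n = p(1 − p)/SE².
- CRT high risk: (73.6 − 57.1)/3.92 = 4.21 points; n ≈ 128.
- RT intermediate risk: (78.2 − 59.4)/3.92 = 4.80 points; n ≈ 93.

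**Simulation with no drug effect.** 40 trial patients against 128 or 93, exponential times, administrative censoring at 1 or 3 years, log-rank at one-sided 0.025. The plan gives no level for the log-rank test, so this one is borrowed from the exact test. With no prognosis gap the test is positive in about 2%.

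| Scenario | Hazard ratio from prognosis alone | Positive |
|---|---|---|
| CRT, 1 year, table's 1-year gap | ln 0.76/ln 0.66 = 0.66 | 18-20% |
| CRT, 3 years, table's 3-year gap | ln 0.57/ln 0.47 = 0.74 | 18-24% |
| RT, residual 72 − 68.8 = 3.2 points, 1 to 3 years | ln 0.72/ln 0.688 = 0.88 | about 4-8% |
| RT, 3 years, table's 3-year gap | ln 0.40/ln 0.37 = 0.92 | about 4% |

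In the CRT 3-year row, the lower end uses the 45.5% 3-year DFS given in section 8.1.2. The upper end extrapolates the 1-year rate, 0.654³ = 28%, which generates more events than that section supports. A smaller shift of 5 points at 1 year gives about 7% in either stratum.

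**The case against.** **The plan is silent; it does not forbid adjustment.** A Cox model can take covariates and none are excluded. A reader might infer that the plan commits to no adjustment. It supports only that none is specified beyond risk group. That still matters, because covariates chosen after the results are seen carry little weight.

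**The gap between two other trials is not this trial's bias.** This stands. A reader might take the 10 to 14 points as an estimate of the error here, but neither its size nor its direction is known. Section 4.1.3 says historical outcomes were lower still without HPV-positive patients, and section 5.1.3 excludes HPV-positive oropharyngeal disease, so bias could also run against the drug.

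**The RT gap is largely covered by the risk split.** This stands too. Moving from the whole RTOG RT arm (58%) to its intermediate-risk subset (68.8%) takes up 10.8 of the 14 points. A reader might add 14 points to 68.8%, which gives false-positive rates of about 38% at 1 year and 65% at 3 years. That counts risk group twice, and the 3-year figure ignores the 3-point gap in the table. The 3.2-point residual is itself only illustrative, since EORTC's 72% is unrestricted.

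**RTOG 9501 was chosen because its entry criteria are said to cover this trial's.** Sections 5.1.2 and 5.3 do not bear that out for intermediate-risk patients with 0-1 nodes. Section 5.3 lets some low-risk patients be withdrawn, but that is discretionary and depends on whether radiation is indicated.

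**The DFS comparison is conditional and supplementary.** True. Power and alpha rest on the exact test. This limits the priority of the point but does not remove it.

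**Conclusion.** The point holds as a gap in specification. If RTOG 9501 records are obtained, the plan would run an unadjusted log-rank test and a Cox model with no stated covariates, no weights and no stated RTOG subset. Nodal count, the factor the protocol itself points to, would be uncontrolled.

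For CRT, restriction to high risk barely moves the benchmark (66% to 65.4%), so a gap like the historical one would persist. The illustrative false-positive rate is about 18-20% at 1 year and 18-24% at 3 years, against a nominal 2.5%. For RT it is roughly 4-8%, provided RTOG patients really are restricted to intermediate risk, which section 8.2.4.2 does not state for the patient-level comparison.

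These figures assume exponential times, historical numbers inferred from confidence intervals, a borrowed significance level, and a prognosis gap taken from two other trials. They show what the method could let through. They do not show that the trial's result will be biased by that amount, and they do not alter the power calculation. This should be corrected, but it does not undermine the primary exact test.

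**What to change.** In sections 8.2.4.2 and 8.2.4.3:

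1. Restrict RTOG 9501 patients to the matching risk group and treatment arm and, where the variables are known, to this trial's entry criteria.
2. Make the main patient-level analysis a Cox model within each risk group, either propensity-weighted or with a short fixed covariate list. Put number of positive nodes first (0-1 versus 2 or more), then T stage and primary site as events allow.
3. Use ECE and margin status as covariates in the high-risk group only. Both are absent by definition in the intermediate group and cannot be adjusted for there.
4. Label the unadjusted log-rank test descriptive.

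The list must be short. At benchmark rates the trial expects about 40 × 0.346 = 14 DFS events by 1 year in the CRT group and 40 × 0.312 = 12 in the RT group. Whether the RTOG file holds each variable cannot be told from the documents, so the text should say what happens if one is missing.

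The cost is a few lines of SAP text, modest analysis work and slightly lower precision. The one-sample exact test stays as it is.
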